^k Following a minimum 14 hr fast, a MMTT will be performed at 0800 ± 15 min on Day -1; baseline blood samples will be collected at T = 0 (alongside samples for other blood tests and 2H labelled glucose); a standardised liquid meal will be given to subjects and consumed in entirety within 5 min. Further blood samples for glucose levels will be collected at T = 15, 30, 45, 60, 120, 180 and 220 min (± 5 min). Note that the start time of the MMTT may be adjusted to 1 hr before or 1 hr after provided all other related procedures are performed at the same time intervals.

^l MRS scans will be performed on Day -1 at 0700, 1300, 2200 (± 15 min) and on Day 1 at 0800 (24 hours post MMTT) (± 15 min). Note that times may be adjusted to 1 hr before or 1 hr after provided all other related procedures are performed at the same time intervals. The MRS scan that will be used to evaluate liver fat content should be performed whilst the subject is fasted and may occur on Day -1 or Day 1.

^m AEs will be assessed from the start of investigational product administration; SAEs will be assessed from the time of signed informed consent form.

ⁿ Injection training should be performed with Placebo MEDI0382 pens prior to Day 1 and with the randomised investigational product on Day 1; subjects should be provided with as much training as they need to be comfortable with self-injection using the pen device between Day -3 through Day 1.

^o On Day -1 or Day 1, subjects will be randomised to receive investigational product: MEDI0382 or placebo or liraglutide. Subjects enrolled in Part A will not be re-enrolled in Part B.

^p A glucose meter, test strips, and a diary should be provided to the subject. The subject should be trained in its use and advised to test their capillary blood glucose at any time the subject feels unwell or has symptoms of hypoglycaemia (hunger, dizziness, shaking, sweating, or irritability) and they should record these symptoms and a capillary plasma glucose level in their diary only when symptomatic. Subjects should do this until their final study visit and bring the diary card with them to their next visit if they recorded symptoms or capillary plasma glucose levels while at home.

^q Investigational product administration should occur in the clinic on Day 1 (Visit 2) after the final MRS scan and blood sample collection (Day 1 first dose of MEDI0382 50 µg or 0.6 mg liraglutide). Daily investigational product administration should then be performed by the subject at home on Day 2 through Day 7 (Day 7 is the last dose of MEDI0382 at a dosage level of 50 µg or liraglutide 0.6 mg). The subject will receive the first dose of MEDI0382 100 µg or liraglutide 1.2 mg in clinic on Day 8 (Visit 3) at any time in the morning. The subject will then self-administer investigational product at home daily on Day 9 through to Day 14 (Day 14 is the last dose of MEDI0382 at a dose level of 100 µg or liraglutide 1.2 mg). On Day 14 or the morning of Day 15 prior to dosing, the site will make remote contact with the subject and remind them to make the up-titration in the MEDI0382 or placebo arms to 200 µg or liraglutide to 1.8 mg and to continue daily dosing at home. On Day 22 subjects in the MEDI0382 or placebo arms will be asked to uptitrate to 300 µg and to continue this dose until their next visit. Subjects in the liraglutide arm will be advised to continue at a dose at 1.8 mg and to continue this dose until their next visit.

^r MEDI0382 or placebo and liraglutide will be dispensed on Days 1 and 8.

^s #Up-titration in blinded arms only

Table 10 Schedule of Treatment Period Study Procedures (Day 32 through Day 36) (Part B)

Visit Number	Outpatient	Treatment Phase				
		V6				
		Inpatient				
Procedure / Study Day	Day 32	Day 33	Day 34	Day 35 ^a	Day 36	
Metformin washout for 5 days ^b	X	X	X	X	X	
Admission to the clinical unit		X				
Assessment of AE/SAEs ^c and review of concomitant medications		X	X	X	X	
Discharge from the clinical unit						X
Fasting overnight for a minimum of 14 hours required			X	X		
Physical examination (abbreviated), ECG, and urine (or serum) pregnancy test		X				
Weight and urinalysis						X
Vital signs (BP, pulse, body temperature, respiratory rate)		X				X
Collection of blood samples for: ^a						
Serum chemistry, haematology, HbA1c, serum calcitonin, amylase, and lipase						X
Fasting amino acids, FFAs, lipids, BHB, acetoacetate and lactate				X		
MEDI0382 Pharmacokinetics ^d				X		
Immunogenicity (ADA) ^e				X		
Blood samples for non-genetic future research ^f				X	X	
Blood samples for ² H labelled glucose ^g			X	X	X	
████████████████ ^h					X	

Table 10 Schedule of Treatment Period Study Procedures (Day 32 through Day 36) (Part B)

Visit Number	Study Period	Outpatient	Treatment Phase			
			V6			
			Inpatient			
Procedure / Study Day	Day 32	Day 33	Day 34	Day 35 ^a	Day 36	
Standardised meals ⁱ		X	X	X		
Deuterated water (2H ₂ O) administration ^j			X			
MMTT and serial blood sampling for glucose levels ^k				X		
Serial MRS scans ^l				X	X	
Investigational product administration in clinic ^m		X	X	X		
Dispense investigational product ⁿ		X				

ADA = anti-drug antibody; AE = adverse event; BHB = beta hydroxybutyrate; BP = blood pressure; ECG = electrocardiogram; eCRF = electronic case report form; FFAs = fasting free fatty acids; HbA1c = glycated haemoglobin; hr = hours; IP = investigational product; min = minutes; MMTT = mixed-meal tolerance test; MRS = magnetic resonance spectroscopy; PK = pharmacokinetic; SAE = serious adverse event; V = Visit.

^a Baseline blood samples (including blood samples for PK) collected on Day 35 should be collected prior to investigational product administration

^b The site should inform the subject to stop taking metformin from the morning of Day 32. Subjects may resume taking metformin on Day 36 after MRS and laboratory assessments on this day.

^c AEs will be assessed from the start of investigational product administration; SAEs will be assessed from the time of signed informed consent form.

^d PK blood sample is to be taken predose on Day 35.

^e ADA samples do not need to be collected in subjects assigned to liraglutide

^f Blood samples for non-genetic testing will be collected on Day 35 and Day 36 at the same time as blood samples are collected for 2H labelled glucose and at T = 0, 220 min (± 5 min), 9 hr (± 30 min), 14 hr (± 30 min) and 24 hr (± 30 min) post morning standardised liquid meal administered at 0800 on Day 35. Note that the time of blood sampling may be adjusted to ± 1 hr provided all other related procedures are performed at the same time intervals.

^g Blood samples for measurement of 2H labelled glucose should be collected just prior to deuterated water administration on Day 34 at 1800 (± 10 min). Further blood samples for measurement of 2H labelled glucose (along with blood samples for non-genetic testing, see footnote e) should be collected on Day 35 and Day 36 following the 0800 morning standardised liquid meal administered on Day 35 at T = 0, 220 min (± 5 min), 9 hr (± 30 min), 14 hr (± 30 min) and 24 hr. Note that the time of sampling may be adjusted to ± 1 hr provided all other related procedures are performed at the same time intervals.

^h [REDACTED]

Table 10 Schedule of Treatment Period Study Procedures (Day 32 through Day 36) (Part B)

Study Period	Visit Number	Treatment Phase				
		Outpatient	V6			
			Inpatient			
Procedure / Study Day		Day 32	Day 33	Day 34	Day 35 ^a	Day 36

ⁱ Standardised solid meals are to be given to subjects 3 times daily on Day 33 and Day 34 at 0900 (\pm 30 min), 1300 (\pm 30 min), and 1700 (\pm 30 min); each meal is to be consumed within 15 minutes. On Day 35, as part of the MMTT, a standardised liquid meal is to be given to subjects in the morning at 0800 (\pm 15 min). Following the MMTT, subjects will be given standardised solid meals for lunch (1400 \pm 5 min) and evening meal (1800 \pm 5 min). Note that the time of standardised meals may be adjusted \pm 1 hr provided all other related procedures are performed at the same time intervals. On Day 35 after the evening meal at 1800 (\pm 5 min), subjects should remain fasted overnight for 14 hours until after the T=24h MRS scan and predose laboratory assessments are performed on Day 36. Subjects are permitted to drink normal water during this period. On Day 36, after the final MRS at 0800 (\pm 15 min), the subject may resume their normal diet.

^j Deuterated water should be administered on Day 34 at 1800 and 2200 (\pm 15 min). The subject should then avoid drinking any additional water until 0800 the next morning. Subjects are permitted to drink small quantities of deuterated water during the fast if thirsty. Note that the start time of the deuterated water administration may be adjusted to 1 hr before or 1 hr after provided all other related procedures are performed at the same time intervals.

^k Following a minimum 14-hour fast, a MMTT will be performed at 0800 (\pm 15 min) on Day 35. Baseline samples will be collected at T = 0 (alongside samples for other blood tests and 2H labelled glucose); a standardised liquid meal will be given to subjects and should be consumed in entirety within 5 min. Further blood samples will be collected at T = 15, 30, 45, 60, 120, 180 and 220 min (\pm 5 min) for 2H labelled glucose levels. Note that the start time of the MMTT may be adjusted \pm 1 hr after provided all other related procedures are performed at the same time intervals.

^l MRS scans will be performed on Day 35 at 0700, 1300 and 2200 (\pm 15 min) and on Day 36 at 0800 (\pm 15 min). Note that times may be adjusted to \pm 1 hr provided all other related procedures are performed at the same time intervals. The MRS scan that will be used to evaluate liver fat content should be performed whilst the subject is fasted and may occur on Day 35 or Day 36.

^m Investigational product administration should occur at home by the subject on Day 9 through 32 and in the clinic at 0800 (\pm 60 min) on Day 33, Day 34, and Day 35. Note that times may be adjusted to \pm 1 hr on Day 35 provided all other related procedures are performed at the same time intervals. Investigational product should be administered on Day 35 just after blood samples have been collected for PK, ADA, 2H labelled glucose, gluconeogenic substrates, and non-genetic research.

ⁿ Investigational product will be dispensed on Day 33

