On the morning of Day 1, following an overnight fast of at least 14 hours, subjects will have a final MRS scan performed (T = 24 hours) and blood sampling. On Day -1 or Day 1, eligibility criteria will be verified (the final eligibility check may occur at any time from Day -3 to Day 1) and subjects will be randomised to receive investigational product (MEDI0382 or placebo in Part A or MEDI0382, placebo, or liraglutide in Part B). Following predose safety measures, the subjects will receive their first dose of investigational product via SC injection and will be discharged from the clinical unit with a sufficient supply of investigational product to self-administer once daily by SC injection at home in the morning.

In Part A subjects will return for an outpatient visit at weekly intervals (Day 8 and Day 15) for safety assessments, dose up-titration until a dose of 300 μg MEDI0382 is reached in Part A. Subjects will receive sufficient supply of investigational product at each outpatient visit.

On Day 26 subjects will be re-admitted to the clinical unit for a further 3 nights inpatient stay and as before will receive standardised solid meals during this period. On the evening of Day 27, subjects will fast and be given $^2\text{H}_2\text{O}$ water to drink at 2 times during the overnight period. On Day 28, following an MRS scan and blood sampling, subjects will receive an SC dose of investigational product and then undergo a MMTT as before at T = 0 and serial MRS scans and blood samples will be collected at T = 4, 9, and 14 hours. On Day 29, following an overnight fast, a final MRS scan will be performed alongside a blood test at T = 24 hours.

In Part B subjects will return for an outpatient visit on Day 8 for safety assessments, dose up-titration, and will receive an adequate supply of investigational product. On Days 14/15 and 21/22 remote contacts will be performed to advise on further dose uptitration as required and to collect AE/serious adverse events (SAEs) and concomitant medication information.

On Day 33 subjects will be re-admitted to the clinical unit for a further 3 nights inpatient stay and as before will receive standardised solid meals during this period. On the evening of Day 34, subjects will fast and be given $^2\text{H}_2\text{O}$ water to drink at 2 times during the overnight period. On Day 35, following an MRS scan and blood sampling, subjects will receive an SC dose of investigational product and then undergo a MMTT as

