2.2 Secondary Objectives and Associated Endpoints

Table 3 Secondary Objectives and Associated Endpoints

Type	Objective	Endpoint
Efficacy	To assess the effect of MEDI0382 on hepatic glycogen levels versus liraglutide after 35 days of treatment (Part B only)	Percentage change in fasting hepatic glycogen concentration adjusted for liver volume as measured by MRS at T = 24 hours post standardised morning meal from baseline (Day 1) to the end of 35 days of treatment (Day 36, Part B only)
Efficacy	To assess the effect of MEDI0382 on hepatic fat fraction versus placebo after 35 days of treatment (Part B only)	Change in hepatic fat fraction from baseline as measured by magnetic resonance imaging (Day -1) to the end of 35 days of treatment (Part B only)
Safety	To evaluate the safety and tolerability of MEDI0382 titrated up to a dose level of 300 µg	Measures of safety and tolerability (vital signs, ECGs, laboratory test results, AEs)
Immunogenicity	To characterise the immunogenicity profile of MEDI0382 titrated up to a dose level of 300 µg	Development of ADA and titre (if confirmed positive)

AE = adverse event; ADA = anti-drug antibodies; ECG = electrocardiogram; MRS = magnetic resonance spectroscopy; T = time.

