4.6.2 Methods to Ensure Blinding

Part A: This is a double-blind study in which MEDI0382 and placebo are not identical in the prefilled syringe titration volumes. Neither the subject nor any of the investigator or sponsor staff who are involved in the treatment or clinical evaluation of the subjects will be aware of the treatment received (ICH E9).

The different fill volumes of investigational product (MEDI0382 and placebo) and the relative position of the plunger rods will be visually distinct during administration. To maintain the blind in Part A, investigational product (MEDI0382 and placebo) prefilled syringes will be handled by an unblinded investigational product manager or unblinded study personnel who will not be involved in the treatment or clinical evaluation of subjects. An unblinded site monitor will perform investigational product accountability, and this will be a different person to the blinded site monitor who will oversee other aspects of the study at the clinical site.

In Part B, the MEDI0382 and placebo multidose pens are indistinguishable. Each subject will know the volume of investigational product they have been instructed to select and administer, the subject and site staff are blinded with respect to whether they are receiving MEDI0382 or placebo. Liraglutide used in Part B will be open-label.

The site will maintain a written plan detailing which staff members are blinded/unblinded and the process of investigational product administration used to maintain the blind.

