4.8.1.1 Analysis Populations

Efficacy Analysis Population

The efficacy analysis will be based on the intent-to-treat (ITT) population, which is defined as all subjects that are randomised and received at least one dose of investigational product, and subjects will be analysed according to randomised treatment assignments. All efficacy analyses will be performed on the ITT population unless otherwise specified.

Safety Analysis Population

The safety analysis will be based on the As-treated population, which includes all subjects who receive at least one dose of any investigational product and subjects will be analysed according to the treatment they actually received.

Pharmacokinetic Analysis Population

The PK population includes all subjects who received at least one dose of investigational product and had at least one PK blood sample taken that is above the lower limit of quantitation.

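### Part B allows randomisation on Day -1, before the Day 1 baseline glycogen scan, so the open-label liraglutide arm can be known while its baseline is being measured

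*Protocol*

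**What the plan says.** Randomisation window. Table 9 (Part B) marks randomisation on both Day -1 and Day 1. Footnote o reads "On Day -1 or Day 1, subjects will be randomised to receive investigational product: MEDI0382 or placebo or liraglutide", and the Study Design part of the synopsis gives the same two days for all arms. The synopsis adds that "the final eligibility check may occur at any time from Day -3 to Day 1".

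Baseline. Protocol Table 3 (section 2.2) defines the liraglutide comparison on fasting glycogen at T = 24 h, "from baseline (Day 1) to the end of 35 days of treatment (Day 36, Part B only"). SAP 3.4.2.2 agrees. Table 9 footnote l times that scan: "and on Day 1 at 0800 (24 hours post MMTT").

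Blinding. Protocol 4.6.1 has the IXRS give the treatment group at the moment of randomisation. Section 4.6.2 states: "Liraglutide used in Part B will be open-label".

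Analysis sets. The ITT population is "all subjects that are randomised and received at least one dose of investigational product" (Protocol 4.8.1.1). Under SAP 3.4.1.2, a subject without a valid baseline scan does not contribute to the analysis.

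Order of events on Day 1. Table 9 footnote q puts the first dose after the final scan and blood sampling. Footnote f waives the predose Day 1 PK and ADA samples for subjects assigned to liraglutide. Nothing in either document requires randomisation to follow the Day 1 scan, or holds the assignment back until then.

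**The concern.** A baseline should be fixed before anyone can know the treatment. Here that holds only if the site chooses to randomise on Day 1 after 0800. If it randomises on Day -1, the liraglutide subject and the staff know the arm before the baseline is complete, while subjects in the other two arms know only that they are in the blinded pair. Adherence to the fast, judgements about whether a scan is valid, and withdrawal before the first dose could then differ by arm.

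The comparison at stake is MEDI0382 against a GLP-1 mono-agonist. Protocol 1.5 points to this kind of contrast as a way of showing glucagon-receptor engagement. Because the endpoint is a percentage change, an error in the baseline enters the denominator. With about 10 subjects per arm, each post-allocation exclusion removes about 1/10 = 10% of an arm.

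The amendment history suggests a carry-over, though this is an inference. The two-day window dates from Amendment 3, and Amendment 5 later moved the endpoint to T = 24 h. The window matters much less in Part A, where both arms are blinded and the primary T = 4 h baseline falls on Day -1.

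**Working it through.** **Timeline for a Part B subject randomised on Day -1** (Table 9 footnotes i, l, o, q)

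| Time | Event | Can the liraglutide arm be known? |
|---|---|---|
| Day -1, 0800 | Liquid meal, T = 0 | Depends on the hour of the IXRS call |
| Day -1, 1800 and 2200 | Evening meal, then T = 14 h scan | Depends on the hour of the IXRS call |
| Overnight | 14 h fast | Yes |
| Day 1, 0800 | T = 24 h scan (endpoint baseline) | Yes |
| Day 1, after scan and samples | First dose | Yes |

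Footnote f shows that the assignment can be acted on before dosing. Protocol 4.8.3.1 labels the Part B primary baseline Day -1, but 24 h after an 0800 meal on Day -1 is 0800 on Day 1, so that label does not remove the problem.

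**The plan's own figure.** The synopsis plans 10 completers per arm, a 24.2-point difference, SD 17.0 and two-sided alpha 0.05. The standard error is 17.0 × √(2/10) = 7.6, and 24.2/7.6 = 3.18. Power is Φ(3.18 − 1.96) = 88.9% by the normal approximation and 85.3% by the noncentral t. The stated figure of above 80% reproduces. It refers to MEDI0382 versus placebo and is not affected by this point.

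**Size of a possible bias.** The documents give no size for a baseline error, so assume the liraglutide baseline is misread by a factor b and the follow-up value is correct.

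1. Unadjusted shift in percentage change: 100 × (1/b − 1). For b = 1.05 this is −4.8 points; for b = 1.10 it is −9.1 points.
2. The planned model adjusts for baseline. If both scans have the same coefficient of variation and correlation r, the slope of percentage change on relative baseline is about −100 × (1 − r). Adjustment therefore gives back about 100 × (1 − r) × (b − 1). The bias left is approximately 100 × (1/b − 1) + 100 × (1 − r) × (b − 1).
3. Results from this formula:

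| r | b = 1.05 | b = 1.10 |
|---|---|---|
| 0.20 | −4.8 + 4.0 = −0.8 | −9.1 + 8.0 = −1.1 |
| 0.38 | −4.8 + 3.1 = −1.7 | −9.1 + 6.2 = −2.9 |
| 0.90 | −4.8 + 0.5 = −4.3 | −9.1 + 1.0 = −8.1 |

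4. The formula is first-order, so the ANCOVA was also simulated with 10 per arm. The coefficient of variation was 41/283 = 14.5% at both scans. That is the Part A planning figure for T = 4 h, borrowed because no T = 24 h figure is visible. A correlation of 0.38 then reproduces the planned SD of 17.0. The bias is about 1.7 points for b = 1.05 and 3.2 points for b = 1.10. Over correlations from 0.2 to 0.9 it runs from 0.8 to 4.3 and from 1.6 to 8.1 points.

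An overstated liraglutide baseline creates a false fall under liraglutide and so shrinks any advantage of MEDI0382; an understated one does the reverse. For a baseline 5% or 10% too low, the unadjusted shifts are +5.3 and +11.1. At r = 0.38 the formula leaves 5.3 − 3.1 = 2.2 and 11.1 − 6.2 = 4.9. Nothing in the documents favours either direction.

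For scale, if the liraglutide arm also has an SD of 17.0 (an assumption), the standard error of the affected comparison before adjustment is the same 7.6 points.

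**The case against.** The case for leaving the window alone has real weight. Day -1 randomisation is permitted, not required. No drug is given before the scan, so the route to bias is behavioural or operational only. Subjects are inpatients on timed standardised meals with a fixed fast, and the endpoint is an instrument reading. Scan procedures are deferred to a study manual that is not among the documents, so rules on repeat scans or blinded reading cannot be presumed absent. Losses between randomisation and dosing would be visible, because SAP 3.3.1 summarises subjects randomised but not treated. Liraglutide is in any case open-label at the Day 36 outcome scan. All of this stands, and it limits the priority. It does not give a reason to keep an avoidable exposure at baseline.

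Four stronger readings are tempting, and the documents do not support them.

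- A reader might take the full 4.8 or 9.1 points as the bias and set it against the 24.2-point planned effect. The planned ANCOVA removes part of the shift, and 24.2 belongs to MEDI0382 versus placebo. No planned effect for the liraglutide comparison is visible.
- A reader might infer that hepatic fat fraction is also affected, since its baseline scan may fall on Day 1. That endpoint is compared with placebo, within the blinded pair.
- A reader might take the eligibility marks on Days -3 to 1 in Table 9 as a required second check after randomisation. They match the window in which one final check may take place. A loss between Day -1 randomisation and Day 1 dosing is possible, but a second check is not shown.
- A reader might conclude that the primary comparison is compromised. Neither of its arms can be told from the other at baseline.

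**Conclusion.** The point holds as a limited design weakness. The permitted order of procedures is certain from the text: in Part B, allocation to an open-label arm can precede the baseline measurement of the endpoint on which that arm is compared. Exclusion from the analysis can also follow knowledge of the arm.

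That material bias would result is not shown. It affects one secondary comparison in an exploratory study, and only for subjects randomised before the 0800 scan on Day 1. The range of roughly 1 to 4 or 2 to 8 points is conditional on an assumed 5% or 10% overstatement of baseline in one arm, equal variability at both scans, and a correlation between 0.2 and 0.9. An error confined to some subjects would give proportionately less. The change is worth making because it is cheap; its priority is low to moderate.

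**What to change.** For Part B, amend the Randomisation row and footnote o of Table 9, and the matching synopsis sentence, so that the IXRS call is made only on Day 1, after the T = 24 h scan has been acquired and the final eligibility check completed, and before the first dose. Delete the Day -1 option. Predose PK and ADA sampling can follow the call, so the liraglutide waiver in footnote f still works.

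The trigger should be that the scan has been acquired. Requiring it to be formally accepted would add a same-morning quality decision, for which the supplied documents give no criterion.

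At the same time, reconcile the Day -1 baseline label for the Part B primary endpoint in Protocol 4.8.3.1 with the Day 1 label used elsewhere.

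Cost: the kit is assigned on the morning of Day 1, and the first dose may come slightly later that morning. Day 1 randomisation, dosing and dispensing are already in the schedule, so no visit, scan or subject is added. The change does not alter the open-label status of liraglutide at the Day 36 scan.
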